8.2 Exclusion Criteria

Patients who meet any of the following criteria are not eligible to participate in the study:

8.2.1 Disease-Related Exclusions:

1. Clinically significant pulmonary hypertension, based on any of the following criteria:
 - a. Receiving treatment for pulmonary arterial hypertension, or
 - b. Evidence for any form of pulmonary hypertension as determined by previous right heart catheterization. Pulmonary arterial hypertension is defined as a mean pulmonary artery pressure ≥ 20 mmHg at rest, a mean pulmonary capillary wedge pressure ≤ 15 mmHg, and the pulmonary vascular resistance ≥ 3 Wood units, or
 - c. Resting transthoracic echocardiography within 6 months of providing written informed consent reporting an estimated right ventricular systolic pressure of >40 mm Hg if subsequent confirmatory right heart catheterization has not been done.
2. Resting transthoracic echocardiography within 6 months of providing written informed consent showing evidence of right atrial or right ventricular enlargement or significant left ventricular dysfunction with left ventricular ejection fraction $< 40\%$
3. Clinical evidence of significant aspiration or uncontrolled gastroesophageal reflux (University of California, Los Angeles, Scleroderma Clinical Trial Consortium Gastrointestinal Tract multi-item scale, 2.0 [UCLA SCTC GIT 2.0] reflux domain score >2.00) [148, 149]
4. Known esophageal dysfunction with esophageal stricture sufficient to limit the ability to swallow oral medication
5. Clinical evidence of significant gastrointestinal involvement (UCLA Scleroderma Clinical Trial Consortium Gastrointestinal Tract multi-item scale 2.0 [UCLA SCTC GIT 2.0] distention/bloating, diarrhea, or social function domain scores >2.00) [148, 149], or evidence of malabsorption.
6. Prior history of renal crisis

8.2.2 Medical Exclusions:

7. Features supporting diagnosis of another connective-tissue disorder (e.g., rheumatoid arthritis or systemic lupus erythematosus)
8. Features supporting diagnosis of another pulmonary disorder (e.g., chronic obstructive pulmonary disease, emphysema, clinically significant adult asthma, or cancer)
9. Clinical evidence of active infection including, but not limited to, bronchitis, pneumonia, sinusitis, or urinary tract infection.
10. History of a clinically significant environmental exposure that is known to cause pulmonary fibrosis including, but not limited to, drugs (e.g., amiodarone), asbestos, beryllium, radiation, or domestic birds or other exposures associated with hypersensitivity pneumonitis
11. Tobacco smoking within 3 months of screening or unwillingness to avoid smoking throughout the study (e.g., cigarette, pipe, or cigar)
12. History of unstable or deteriorating cardiac disease within the previous 6 months relative to study Day 1 including, but not limited to, the following:
 - a. Unstable angina pectoris
 - b. Myocardial infarction
 - c. Congestive heart failure requiring hospitalization
 - d. Uncontrolled clinically significant arrhythmia
 - e. Clinically significant pericardial effusion
 - f. Pulmonary hypertension (see 8.2.1 Exclusion Criteria - Disease Related)
13. Known underlying liver disease (e.g., hepatitis or cirrhosis)
14. Known or suspected peptic ulcer
15. Known active hematologic disorder other than anemia of chronic disease or iron deficiency anemia (hemoglobin < 8.0 gm/dl).
16. Known hematologic malignancy
17. History of any malignancy within the last 5 years other than non-melanoma skin cell cancers cured by local resection or carcinoma-in-situ
18. Prior stem cell or bone marrow transplant
19. Any condition that might be significantly exacerbated by the known side effects associated with ixazomib including known \geq grade 2 peripheral neuropathy
20. Pregnancy or lactation: Positive pregnancy test; currently lactating; or for women of childbearing potential and men, an unwillingness to maintain abstinence or highly effective contraception (see 8.1.3 Eligibility Criteria – Informed Consent and Protocol Adherence)

21. History of alcohol or substance abuse in the previous 2 years relative to study Day 1.
22. Expected to have study participation interrupted for a foreseeable medical or surgical event (e.g., organ, stem cell, or bone marrow transplant; orthopedic-related surgery).
23. Any condition that is likely to result in the death of the patient within 12 months.
24. History of known or active COVID19 infection.

8.2.3 Laboratory Exclusions:

25. Any of the following screening test criteria:
 - a. Hemoglobin \leq 8.0 gm/dl
 - b. Absolute neutrophil count \leq 1000
 - c. Platelet count \leq 75,000
 - d. Total bilirubin above $1.5 \times$ upper limit of the normal range (ULN), except in patients with predominantly unconjugated hyperbilirubinemia (e.g., Gilbert's syndrome)
 - e. Aspartate or alanine aminotransferase (AST or ALT) $>2 \times$ ULN
 - f. Alkaline phosphatase $>2 \times$ ULN
 - g. Creatinine clearance <30 mL/min

8.2.4 Medication Exclusions:

26. Any prior use of ixazomib or other proteasome inhibitor
27. Any prior use of rituximab
28. Any prior use of cyclophosphamide
29. Suspected intolerance, allergy, or hypersensitivity to ixazomib or any of its excipients
30. Ongoing use or expected use of any of the following therapies:
 - a. Investigational drug within the 28 days before screening (an investigational drug is defined as any drug that has not been FDA approved for marketing)
 - b. Strong CYP3A inducers (e.g. rifampin, rifapentine, rifabutin, carbamazepine, enzalutamide, phenytoin, fosphenytoin, phenobarbital, St. John's wort)
 - c. Methotrexate
 - d. Leflunomide
 - e. Azathioprine
 - f. Sirolimus
 - g. Tacrolimus
 - h. Oral corticosteroids at a dose >10 mg/d prednisone equivalent
 - i. D-penicillamine
 - j. Minocycline
 - k. Interferon- γ

- i. Endothelin-1 receptor antagonists (e.g., bosentan, ambrisentan or macitentan)
- m. Phosphodiesterase inhibitors (for use other than erectile dysfunction or Raynaud's phenomenon)
- n. Riociguat
- o. Tumor necrosis factor- α (TNF- α) inhibitor drugs
- p. Tocilizumab
- q. Rituximab
- r. Abatacept
- s. Cyclosporine
- t. Cyclophosphamide
- u. Intravenous immunoglobulin (IVIG)
- v. Nintedanib

8.2.5 General Exclusion:

- 31. Unsuitable for enrollment or unlikely to comply with study requirements, as assessed by the investigator

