17.2.5 Echocardiogram

If a resting transthoracic echocardiogram has not been done within 6 months prior to written informed consent at medication washout or screening, as applicable, it will be performed at screening.

17.2.6 University of California, Los Angeles, Scleroderma Clinical Trials Consortium Gastrointestinal Scale, 2.0, Questionnaire [148, 149]

The UCLA Scleroderma Clinical Trials Consortium Gastrointestinal Tract (UCLA SCTC GIT) 2.0 is a self-administered survey. The survey consists of 34 questions (Reflux 1 to 8, Distention/Bloating 9 to 12, Fecal Soilage 13, Diarrhea 14 to 15, Social functioning 16 to 21, Emotional well-being 22 to 30, Constipation 31 to 34). The items are scored on a scale from 0 to 3, where 0 indicates better health and 3 indicates worse health, except for questions 15 and 31, which are scored as 0 (better health) and 1 (worse health). Scores from all scales except the constipation scale are averaged to form a total GIT score from 0 (no gastrointestinal problems) to 3 (most severe) that captures overall burden of severity of SSc-associated GIT involvement.

The UCLA SCTC GIT 2.0 questionnaire will be used to obtain the participant's assessment of

the frequency of GI symptoms in the preceding 7 days and how those symptoms affected his/her life. The questionnaire will be administered during screening (see 8.2.1 Study Population Exclusion Criteria), at study Day 1, and at each subsequent study visit every 28 days (weeks 4-24). For the extension study, the questionnaire will be administered at study day 84 (week 36) and study day 168 (week 48) office visits.

17.3 Study Measures for the Secondary Objective to Assess the Clinical Efficacy of Ixazomib

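### With domain scores as item means, the printed GIT 2.0 scoring caps the diarrhea score at exactly 2.00, so the diarrhea exclusion (above 2.00) cannot be met, and the stated total maximum of 3 is not reproduced

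*Combined protocol and SAP*

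**What the plan says.** Section 8.2.1 uses GIT 2.0 domain scores as exclusions in two places. Criterion 3 uses a "reflux domain score >2.00". Criterion 5 uses "distention/bloating, diarrhea, or social function domain scores >2.00", "or evidence of malabsorption". Both inequalities are strict.

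Section 17.2.6 describes the instrument. It lists 34 items and assigns them to scales, including "Diarrhea 14 to 15, Social functioning 16 to 21". Items run from 0 to 3, "except for questions 15 and 31, which are scored as 0 (better health) and 1 (worse health"). All scales except constipation are "averaged to form a total GIT score from 0 (no gastrointestinal problems) to 3 (most severe"). The section ties the scoring to eligibility: "The questionnaire will be administered during screening (see 8.2.1 Study Population Exclusion Criteria").

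No section says how a domain score is built from its items, or what to do when an item is left blank.

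**The concern.** The diarrhea domain has only two items, and one of them cannot score above 1. A cut-off that is ordinary for a domain made of 0-to-3 items may therefore lie at or beyond the top of this one. Because the inequality is strict, a maximum of exactly 2.00 makes the rule empty.

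Two things are at stake.

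- **Eligibility.** Section 9.2.1 lists diarrhea among the reactions associated with ixazomib, and section 5.0 says that the gastrointestinal safety profiles of ixazomib and MMF overlap. The plan chose a diarrhea score as a screening exclusion. If that score cannot pass the cut-off, a candidate giving the worst answer to both diarrhea questions is not excluded by the rule written for that purpose.
- **Analysis.** The questionnaire is a named measure for the primary safety objective (section 6.1) and is summarised in section 24.5. The domain formula is needed there too.

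**Working it through.** **Inputs, all from section 17.2.6 unless noted**

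- Items per scale: reflux 8, distention/bloating 4, fecal soilage 1, diarrhea 2 (items 14 and 15), social functioning 6, emotional well-being 9, constipation 4. These add to 34, as stated.
- Item maximum: 3, except items 15 and 31, where it is 1.
- Total: the average of the six scales other than constipation, with a stated maximum of 3.
- Cut-off: strictly above 2.00 (section 8.2.1).
- Assumption: a domain score is the mean of its items. The plan does not state this.

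**Step 1. The plan's own figure, a total maximum of 3**

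Under item means, five of the six scales have a maximum of 3. Diarrhea has (3 + 1)/2 = 2.00. The total maximum is (5 × 3 + 2)/6 = 17/6 = 2.83.

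Other readings:

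- Pooling the same 30 items: (29 × 3 + 1)/30 = 88/30 = 2.93.
- Domain scores as sums: (24 + 12 + 3 + 4 + 18 + 27)/6 = 88/6 = 14.67, far outside the stated range.

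None of these gives 3. Sums clearly do not fit, which is why the item mean is the natural reading.

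**Step 2. Can the diarrhea score exceed 2.00?**

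Item 14 has four values and item 15 has two, so there are 8 answer pairs. Their means take the values 0, 0.5, 1.0, 1.5 and 2.0. Pairs above 2.00: 0 of 8. Pairs equal to 2.00: 1 of 8 (item 14 = 3, item 15 = 1).

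**Step 3. Does the cut-off work in the other domains?**

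Yes. Each has a maximum of 3.00. The answer patterns with a mean above 2.00 are:

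- distention/bloating: 35 of 4^4 = 256 (13.7%)
- social functioning: 420 of 4^6 = 4,096 (10.3%)
- reflux: 5,115 of 4^8 = 65,536 (7.8%)

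These are counts of possible answers, not of patients. They show only that the cut-off can be reached there.

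**Step 4. What would make the text consistent?**

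Let q be the most that item 15 can contribute. Then the diarrhea maximum is (3 + q)/2 and the total maximum is [15 + (3 + q)/2]/6.

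| q | Diarrhea maximum | Total maximum | Pairs above 2.00 |
|---|---|---|---|
| 1 (as printed) | 2.00 | 2.83 | 0 of 8 |
| 2 | 2.50 | 2.92 | 1 of 8 |
| 3 | 3.00 | 3.00 | 2 of 8 |

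Exceeding 2.00 needs q above 1. A total maximum of 3 needs q = 3. Both mismatches therefore come from one source, the 0/1 scoring of item 15.

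**Step 5. Effect on the safety summaries**

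For anyone who scores 1 on item 15, moving from q = 1 to q = 3 raises the diarrhea score by (3 − 1)/2 = 1.00 and the total by 1.00/6 = 0.17.

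**The case against.** The strongest reply is that the plan never states the item-mean rule. Sections 8.2.1 and 17.2.6 cite published references for the instrument, and the full scoring may be there. Moreover, the only variant above that gives the stated total of 3 is q = 3, and at q = 3 criterion 5 works as written. On that view the proven slip is in 17.2.6, and the empty exclusion is only a possible consequence.

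This is fair as far as it goes. The documents do not show whether the slip lies in the scoring text or in the criterion, and the conclusion is conditional for that reason. But 17.2.6 prints specific item scores, and nothing tells the site to rescale item 15. A coordinator who applies the printed scores and takes item means gets a diarrhea rule that cannot be triggered.

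Three smaller points also stand.

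- If item 15 is left blank and the mean is taken over answered items, item 14 alone could give 3. The result therefore assumes that both items are answered.
- The gap between 2.83 and 3 changes no decision by itself. No eligibility criterion uses the total, and section 24.2 plans no formal hypothesis testing.
- The consequence is small. The distention/bloating, social function and malabsorption parts of criterion 5 remain, as do criteria 19 and 31, and section 9.2.3.4 has a rule for grade 2 or 3 events on study. The questionnaire is also patient-reported ("2.0 is a self-administered survey") and is not the only route by which severe diarrhea would come to light.

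**Conclusion.** The point holds. Under item means, with both items answered and scored as printed, the diarrhea part of criterion 5 cannot be met (0 of 8 answer pairs), and the total runs to 2.83 where the plan states 3. The printed item scores, the printed total range and the exclusion cut-off do not agree with one another.

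The item-mean assumption is not stated in the plan, but sums are ruled out by the 0-to-3 total. Which of the texts is in error cannot be settled from the documents. How many candidates would be affected is unknown. This should be corrected, but it does not threaten the study's main conclusions.

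**What to change.** Reconcile the two sections in this order.

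1. In 17.2.6, state how items form a domain score, including what happens when an item is missing. Make the item 15 scoring and the stated total maximum agree.
2. Check criterion 5 against the resulting diarrhea range.
   - If item 15 stays at 0 or 1, the total maximum becomes 2.83 and the diarrhea maximum stays at 2.00. The diarrhea part of criterion 5 is then still unattainable, and the investigator needs to restate it to fit that range. The choice of threshold is a clinical one and is not proposed here.
   - If item 15 counts as 0 or 3, both maxima are 3.00 and criterion 5 needs no change.
3. Use the same formula for the GIT 2.0 summaries in sections 24.5 and 25.5.1.

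The cost is one sentence in 17.2.6 (two with the missing-item rule) and, in the first case only, one phrase in criterion 5. The possible downside is that a working diarrhea exclusion could screen out some candidates from a study that plans only 12 patients. The documents give no basis for estimating how many.

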9.0 STUDY TREATMENT

9.1 Ixazomib Dosing Regimen, Administration, and Handling

Ixazomib will be supplied by Takeda as capsules of 2.3mg, 3mg, and 4.0 mg. All patients will be given oral ixazomib during the study. The dosing will be 4 mg orally on days 1, 8, and 15 of a 28-day treatment cycle for 6 cycles. The first dose of ixazomib will be taken on study Day 1.

9.1.1 Dosing Guidelines:

- Each dose is to be taken at the same time of day.
- Dosing should be 1 hour before or at least 2 hours after food.
- The capsule is to be swallowed whole with a total of approximately 8 ounces (240 mL) of water; it should not be opened, crushed, or chewed.
- A missed dose should be taken only if the next scheduled dose is at least 72 hours away; otherwise, the missed dose is to be skipped and participant instructed to take the next scheduled dose.
- A repeat dose should not be taken if vomiting occurs; the participant is to continue therapy with next scheduled dose.

9.1.2 Precautionary Measures:

- As Ixazomib is cytotoxic, direct contact with capsule contents is to be avoided. Study participants will use single gloves when handling intact capsules.
- If capsule breakage occurs, study participants should avoid direct contact of contents with the skin or eyes. If contact occurs with the skin, it should be washed thoroughly with soap and water. If contact occurs with the eyes, they should be flushed thoroughly with water.
- Dispose properly any unused medicinal product or waste material.

- Participants who have some symptoms of gastroesophageal reflux but do not meet the disease-related exclusion criterion can be enrolled, but will be advised on ways to manage the symptoms with life-style changes (e.g., avoid reclining after a meal, not eating within 3 hours of retiring at night, elevate the head of the bed 4-6 inches, and avoidance certain foods). Any medication required to manage GI reflux/symptoms will be commenced before the start of ixazomib treatment on study Day 1.

9.2 Ixazomib Dose Modification or Interruption

9.2.1 Management of Clinical Events

Adverse drug reactions such as thrombocytopenia, diarrhea, fatigue, nausea, vomiting, and rash have been associated with ixazomib treatment. Further details of management of ixazomib AEs are described in the ixazomib IB [143].

Ixazomib dose modification or interruption will be allowed for safety or tolerability reasons at any time during the study at the discretion of the investigator. In general, if dose modification is necessary, the first ixazomib dose reduction is to 3 mg; second dose reduction is to 2.3 mg; and thereafter, to discontinue use.

9.2.2 Hematologic toxicity

9.2.2.1 In the event of absolute neutrophil count $\leq 1000/\text{mm}^3$, ixazomib dose will be managed as follows:

1. Ixazomib administration will be interrupted and paused until the absolute neutrophil count (ANC) is $> 1000/\text{mm}^3$ upon retesting of the CBC weekly or sooner as clinically indicated.
2. G-CSF administration may be considered as clinically indicated.
3. Upon recovery of the ANC $> 1000/\text{mm}^3$, ixazomib administration may resume at the first reduction dose of 3 mg with weekly monitoring of CBC for the remainder of that study cycle until the next study visit. The 3 mg dose should follow the dose cycle schedule for the remainder of that study visit and subsequent study visits unless recurrent ANC $\leq 1000/\text{mm}^3$ occurs.
4. In that instance, ixazomib administration will be interrupted and paused until the ANC has recovered $> 1000/\text{mm}^3$ upon retesting of the CBC weekly or sooner as clinically indicated.
5. G-CSF administration may be considered again as clinically indicated.
6. Upon recovery of the ANC $> 1000/\text{mm}^3$, ixazomib administration may resume at the second reduction dose of 2.3 mg with weekly monitoring of CBC for the remainder of that study cycle until the next study visit. The 2.3 mg dose should follow the dose cycle schedule for the remainder of that study visit and subsequent study visits unless recurrent ANC $\leq 1000/\text{mm}^3$ occurs.
7. In that instance, ixazomib administration will be discontinued. A CBC will be monitored weekly or sooner if clinically indicated until the ANC has recovered to $> 1000/\text{mm}^3$. The participant will be discontinued from the study and will proceed to complete assessments and procedures for early discontinuation (See 15.0 Early Discontinuation).

9.2.2.2 In the event of platelet count $\leq 30,000 \text{ mm}^3$, ixazomib dose will be managed as follows:

- **If thrombocytopenia is asymptomatic or associated with petechiae/bruising without other significant bleeding:**
 1. Ixazomib administration will be interrupted and paused until the platelet count is $\geq 50,000/\text{mm}^3$ upon retesting of the CBC daily and then weekly until the platelet count is $\geq 75,000/\text{mm}^3$.
 2. Upon recovery of the platelets $\geq 75,000/\text{mm}^3$ ixazomib administration may resume at the first reduction dose of 3 mg with weekly monitoring of CBC for the remainder of that study cycle until the next study visit. The 3 mg dose should follow the dose cycle schedule for the remainder of that study visit and subsequent study visits unless recurrent thrombocytopenia $\leq 30,000/\text{mm}^3$ occurs.
 3. In that instance, if thrombocytopenia is asymptomatic or associated with petechiae /bruising without other significant bleeding, ixazomib administration will be interrupted and paused until the platelet count is $\geq 50,000/\text{mm}^3$ upon retesting of the CBC daily and then weekly until the platelet count is $\geq 75,000/\text{mm}^3$.
 4. Upon recovery of the platelets $\geq 75,000/\text{mm}^3$, ixazomib administration may resume at the second reduction dose of 2.3 mg with weekly monitoring of CBC for the remainder of that study cycle until the next study visit. The 2.3 mg dose should follow the dose cycle schedule for the remainder of that study visit and subsequent study visits unless recurrent thrombocytopenia $\leq 30,000/\text{mm}^3$ occurs.
 5. In that instance, ixazomib administration will be discontinued. If thrombocytopenia is asymptomatic or associated with petechiae/ bruising without other significant bleeding, the thrombocytopenia will be monitored with a CBC daily until the platelet count is $\geq 50,000/\text{mm}^3$ and then weekly until the platelet count has returned to $\geq 75,000/\text{mm}^3$. The participant will be discontinued from the study and will proceed to complete assessments and procedures for early discontinuation (See 15.0 Early Discontinuation).

9.2.3 Non-Hematologic toxicity:

9.2.3.1 In the event of either new or worsening baseline peripheral neuropathy, ixazomib dose will be managed as follows:

- **If grade 1 (mild) new peripheral neuropathy with pain or worsening baseline peripheral neuropathy grade 2 (moderate):**
 1. Ixazomib administration will be interrupted and paused until the peripheral neuropathy is grade 1 or lower without pain, or at patient's baseline.
 2. If recovery of the neuropathy has occurred, ixazomib administration may resume at the first reduction dose of 3 mg and should follow the dosecycle schedule for the remainder of that study visit and subsequent study visits unless recurrent worsening neuropathy occurs.
 3. In that instance, if return of grade 1 peripheral neuropathy with pain or worsening again of baseline peripheral neuropathy grade 2, ixazomib

administration will be interrupted and paused until the peripheral neuropathy is grade 1 or lower without pain, or at patient's baseline.

4. If improvement of the neuropathy has occurred, ixazomib administration may resume at the second reduction dose of 2.3 mg and should follow the dose cycle schedule for the remainder of that study visit and subsequent study visits unless any recurrent or worsening of baseline neuropathy occurs.
5. In that instance, ixazomib administration will be discontinued. The participant will be discontinued from the study and will proceed to complete assessments and procedures for early discontinuation (See 15.0 Early Discontinuation).

- **If grade 2 (moderate) new peripheral neuropathy with pain**
 1. Ixazomib administration will be interrupted and paused until the peripheral neuropathy is grade 1 or lower without pain, or at patient's baseline.
 2. If improvement of the neuropathy has occurred, ixazomib administration may resume at the first reduction dose of 3 mg and should follow the dose cycle schedule for the remainder of that study visit and subsequent study visits unless recurrent worsening neuropathy occurs.
 3. In that instance, if return of grade 2 peripheral neuropathy with pain, ixazomib administration will be interrupted and paused until the peripheral neuropathy is grade 1 or lower without pain, or at patient's baseline.
 4. If improvement of the neuropathy has occurred, ixazomib administration may resume at the second reduction dose of 2.3 mg and should follow the dose cycle schedule for the remainder of that study visit and subsequent study visits unless any recurrent or worsening of baseline neuropathy occurs.
 5. In that instance, ixazomib administration will be discontinued. The participant will be discontinued from the study and will proceed to complete assessments and procedures for early discontinuation (See 15.0 Early Discontinuation).
- **If grade 3 (severe) new peripheral neuropathy with pain or worsening baseline peripheral neuropathy to grade 3 (severe)**
 1. Ixazomib administration will be discontinued. The participant will be discontinued from the study and will proceed to complete assessments and procedures for early discontinuation (See 15.0 Early Discontinuation).

9.2.3.2 In the event of either new or worsening rash, ixazomib dose will be managed as follows:

- **If new grade 1 (mild) or 2 (moderate) rash for which there is no other immediate explanation** ixazomib dose will be managed as follows:
 1. Ixazomib administration will be interrupted and paused until the rash is grade improved grade 1 or resolved if grade 1.
 2. Upon improvement of the rash, ixazomib administration may resume at the first reduction dose of 3 mg and should follow the dose cycle schedule for the remainder of that study visit and subsequent study visits unless any recurrent or worsening of baseline rash occurs.

remainder of that study visit and subsequent study visits unless recurrent rash grade 2 occurs.

3. In that instance, ixazomib administration will be interrupted and paused until the rash is improved grade 1 or resolved if grade 1.
4. Upon improvement of the rash, ixazomib administration may resume at the second dose reduction dose of 2.3 mg and should follow the dose cycle schedule for the remainder of that study visit and subsequent study visits unless recurrent rash grade 2 occurs.
5. In that instance, ixazomib administration will be discontinued. The participant will be monitored until the rash is improved grade 1 or resolved. The participant will be discontinued from the study and will proceed to complete assessments and procedures for early discontinuation (See 15.0 Early Discontinuation).

- **If grade 3 (severe) rash for which there is no other immediate explanation** ixazomib dose will be managed as follows:

1. Ixazomib administration will be discontinued. The participant will be monitored until the rash is improved grade 1 or resolved. The participant will be discontinued from the study and will proceed to complete assessments and procedures for early discontinuation (See 15.0 Early Discontinuation).

9.2.3.3 In the event of hepatic impairment ixazomib dose will be managed as follows:

- If serum alkaline phosphatase is not more than 2 X upper limited of normal (ULN); total bilirubin is not greater than 1.5 X ULN except in patients with predominantly unconjugated hyperbilirubinemia (e.g., Gilbert's syndrome), and AST or ALT is not more than 2 X ULN, ixazomib dose will be managed as follows:
 1. Ixazomib administration will be revised to the first reduction dose of 3 mg and should follow the dose cycle schedule for the remainder of that study visit with weekly monitoring of alkaline phosphatase, total and indirect bilirubin, and AST or ALT for the remainder of that study cycle until the next study visit. The 3 mg dose should follow the dose cycle schedule for the remainder of that study visit and subsequent study visits unless worsening of liver function tests is observed.
- If serum alkaline phosphatase is greater than 2 X upper limited of normal (ULN), total bilirubin is greater than 1.5 X ULN except in patients with predominantly unconjugated hyperbilirubinemia (e.g., Gilbert's syndrome), and AST or ALT is more than 2 X ULN, ixazomib dose will be managed as follows:
 1. Ixazomib administration will be discontinued. The participant will be monitored weekly until the liver function tests return to baseline or resolve. The participant will be discontinued from the study and will proceed to complete assessments and procedures for early discontinuation (See 15.0 Early Discontinuation).

9.2.3.4 If other nonhematologic adverse events, grade 2 or 3, ixazomib dose will be managed as follows:

1. Ixazomib administration will be interrupted and paused until the adverse event has improved to grade 1 or resolved.

2. Supportive care for the adverse event may be considered as clinically indicated.
3. Upon improvement of the adverse event to grade 1 or resolution, ixazomib administration may resume at the first reduction dose of 3 mg and should follow the dose cycle schedule for the remainder of that study visit and subsequent study visits unless a recurrent adverse event grade 2 or 3 of the same nature occurs.
4. In that instance, ixazomib administration will be interrupted and paused until the adverse event has improved to grade 1 or resolved.
5. Upon improvement of the adverse event to grade 1 or resolution, ixazomib administration may resume at the second reduction dose of 2.3 mg and should follow the dose cycle schedule for the remainder of that study visit and subsequent study visits unless a recurrent adverse event grade 2 or 3 of the same nature occurs.
6. In that instance, ixazomib administration will be discontinued. Supportive care for the adverse event may be considered as clinically indicated. The participant will be discontinued from the study and will proceed to complete assessments and procedures for early discontinuation (See 15.0 Early Discontinuation).

If participants require hospitalization, consideration will be given to continuing study treatment, if appropriate. If the participant is hospitalized at an institution other than Mayo Clinic Hospital, the treating physician will be encouraged to discuss the patient's management with a Mayo investigator at the earliest possible time. All records pertaining to the hospitalization will be obtained.

